5.2 Treatment

After completing all screening activities, patients confirmed to be eligible will enter the study and receive the following treatments and visits: new adjuvant treatment with vidicon combined with piAmpley monoclonal antibody (up to 4 dosing cycles), once every 3 weeks; The patient underwent radical cystectomy after neoadjuvant chemotherapy; The patient's complete pathological response rate, phase reduction rate, and regular follow-up of two years were detected postoperatively to evaluate the patient's drug/surgical safety and to evaluate the survival of the patient's radical resection after neoadjuvant immunization combined with chemotherapy.

New adjuvant regimens (up to 4 cycles administered): 2.0mg/kg, Vidisituzumab on Day 1, administered intravenously, Ampley monoclonal, 200mg, administered intravenously on Day 1 of each 21-day cycle. Order of use: Vidicidone monoclonal antibody → PyAmpley monoclonal antibody.

Surgical scheme: radical cystectomy+urinary diversion.

Specific treatment and visit designs are as follows.

5.2.1 Screening period

Screening phase evaluation will be conducted within 28 days prior to enrollment and the patient has been diagnosed with transurethral resection of bladder tumor (TURBT) or cystoscopy biopsy; Patients who agree to participate in this study will sign an Informed Consent Form (ICF) prior to undergoing any screening procedures. Radical cystectomy must be performed at baseline at the investigator's discretion following neoadjuvant treatment. Screening assessment in the screening period can be repeated as needed; The investigator will initially assess the patient's eligibility based on the most recent screening assessments.

5.2.2 Drug treatment period

Upon completion of all screening activities, patients confirmed to be eligible will enter the study and receive treatment as follows: up to 4 cycles of administration of vidicon in combination with Ampley monoclonal antibody).

Imaging evaluation will be performed before the start of cycle 3 of new adjuvant therapy, and if the patient does not develop PD, treatment will be continued as planned; If the patient had PD, subsequent treatment would be administered at the discretion of the investigator.

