
research centre
 
Sun yat-sen university memorial hospital The Third Affiliated Hospital of Sun Yat-sen University Southern hospital of southern medical university Zhujiang hospital of southern medical university The Third Affiliated Hospital of Southern Medical University

Efficacy evaluation
 
Imaging evaluation by independent review experts according to the specific situation of patients, determine the evaluation time and evaluation method.

Data management and statistical analysis
 
SAS 9.4 statistical software was used for statistical analysis. Unless otherwise specified, all statistical tests will use a one-sided test with $\alpha=0.05$ and the confidence intervals will use a one-sided 95% confidence interval.

Estimated Start and End Time: Start Time: June 2022; End: April 2026

II. introduction

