In this study, we intended to add immunotherapy to the treatment of patients with locally advanced urothelial carcinoma of the bladder who were intolerant to locally advanced cisplatin, so as to obtain the efficacy and safety indicators for the platinum-intolerant patients with locally advanced urothelial carcinoma of the bladder treated with the neoadjuvant therapy of vidicon combined with Ampley monoclonal antibody, and to provide guidance for the follow-up Phase III clinical trial and clinical application.

III. Study purpose and endpoint

1. Research purposes

1.1 Main research objectives:

To evaluate the pathological complete response rate (pCR rate) after radical cystectomy in patients with HER2 expression, cisplatin-intolerant cT2-T4aNxM0 vesical urothelial carcinoma treated with neoadjuvant therapy of vidicon combined with Ampley monoclonal antibody.

1.2 Secondary study objectives:

A) Evaluating the pathological descending rate;

B) Evaluating event-free survival (EFS);

C) Evaluating overall survival (OS);

D) To evaluate the safety of the new adjuvant therapy and its impact on radical cystectomy (evaluated according to NCI-CTCAE v5 and surgical complications according to Clavien-Dindo scoring criteria).

2. Analysis set:

2.1 Safety analysis set: Includes all patients who received at least 1 dose of any study drug (any component of neoadjuvant combination therapy).

2.2 Effectiveness analysis set: Includes all patients who received at least 1 dose of any study drug treatment (any component of neoadjuvant combination therapy) and had a radical cystectomy following that treatment.

3. Observation indicators

3.1 Main indicators:

Pathological complete response rate (pCR rate): the pathological stage after radical cystectomy was pT0N0 (based on effectiveness analysis)

3.2 Secondary indicators:

A) Pathological decline rate: the proportion of patients with pathological stage \leq pT1N0 (based on the efficacy analysis set) after radical cystectomy;

B) Safety: to evaluate the safety and impact on radical cystectomy of the new adjuvant therapy (evaluated according to NCI-CTCAE v5 and surgical complications according to Clavien-Dindo scoring criteria) (based on the safety analysis set);

C) Event-free survival (EFS): EFS is defined as the time from enrollment to disease progression, death from any cause, or new onset of another tumor.

D) Total survival (OS): Total survival was defined as the time from enrollment to death for any cause.

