3. The investigator judges that the operation timing is delayed, including but not limited to: disease progression occurs in the new adjuvant treatment stage or AE fails to complete 4 cycles of new adjuvant treatment, and the operation is not performed although it is assessed by the investigator to be in line with the indications for radical surgery;
4. Combined use of any anti-tumor therapy;
5. Patients fail to comply.

Patient withdrawal (individual patient ends the study): A patient may withdraw from the study for the following reasons, including but not limited to the following: 1. The patient withdraws informed consent; 2. Death; 3. Loss of follow-up.

V. research design

5.1 overall design

This is a multicenter, open-label, single-arm prospective clinical study to evaluate the efficacy and safety of neoadjuvant treatment with vidicon and Ampley monoclonal antibody in patients with cisplatin-intolerant cT2-T4aNxM0 urothelial carcinoma of the urinary bladder. In the absence of active withdrawal from the trial, intolerable drug-induced toxic and side effects, or findings that the subject was considered by the investigator to be unsuitable for further trials, each subject will undergo post-treatment surgery according to the following protocol, with efficacy evaluation and follow-up at each cycle.

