5.2.4 Surgical treatment

Preoperative evaluation will be performed prior to radical surgery, and if the patient meets the surgical indications, the investigator will perform radical cystectomy at an appropriate time as planned; If the patient is not suitable for surgery, the investigator decides to administer subsequent treatment. Disease progression occurs during the neoadjuvant treatment phase, or the AE fails to complete 4 cycles of neoadjuvant treatment (total neoadjuvant treatment duration does not exceed 15 weeks), but if the investigator assesses that the indication for radical surgery is met, surgery will be continued within the specified time frame and will still be considered eligible for treatment and evaluation for all study requirements. If the investigator determines that physical conditions preclude radical surgery, study treatment will be discontinued, an end-of-treatment visit will be given, and additional treatment selected by the investigator will be continued. If any of the conditions exceed the above time limits, but the investigator determines that the procedure is still acceptable, the team

leader unit will be contacted to determine whether or not they are eligible for study analysis. Patients who discontinue neoadjuvant therapy early due to disease progression or an intolerable adverse event (AE) before surgery and do not undergo surgery are given an end-of-treatment visit and will continue to receive other treatments selected by the investigator.

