5.4 Statistical analysis

5.4.1 Sample size and calculation basis

The historical control pCR rate was assumed to be 10% based on recent clinical studies. The expected pCR estimate for this study was 25%, representing a clinically significant improvement. The resulting zero and alternative assumptions are as follows:

The original assumptions to be tested were: h_0 : PCR rate = 25%

Corresponding alternative hypothesis: h_a : pcr rate > 25%

The Simon Phase II (Simon, 1989) design will be used to test the superiority of the combination

of neoadjuvant therapy with Ampley monoclonal antibody as compared with the historical control. The expected Class I error rate for the project (ineffective study drug but effective promotion) $\alpha=0.05$, with 80% confidence. An interim efficacy and safety analysis will be performed when 18 subjects are enrolled. Of the 18 subjects in the first phase, the second phase was not performed if < 2 effective cases of complete pathological response were achieved. If there were ≥ 2 valid cases in Phase 1, continue with Phase 2 until there are a total of 43 subjects. If the total effective cases in the first and second stages were not less than 7, it could be determined that the pCR of the new adjuvant therapy in this study was significantly improved compared with the historical control, thereby demonstrating the superiority and efficacy of the new adjuvant therapy in this study. A 10% dropout rate was considered for this study, which required the recruitment of a total of 48 subjects. The statistical design was calculated using an online statistical tool approved by the Design Department of Sun Yat-sen Memorial Hospital, Sun Yat-sen University (<http://cancer.unc.edu/biostatistics/program/ivanova/simonstwostageDesign.aspx>) (Ivanova & Deal, 2016).

5.4.2 data analysis set

Safety analysis set: Includes all patients who received at least 1 dose of any study drug (any component of neoadjuvant combination therapy).

Efficacy analysis set: Includes all patients who received at least 1 dose of any study drug treatment (any component of neoadjuvant combination therapy) followed by radical cystectomy.

5.6.3 Statistical analysis plan.

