6.2 Combined treatment (permitted adjuvant, supplemental/alternative therapies)

All concomitant medications during the study (generic name of the drug, purpose of administration, dose administered, time of administration, etc.) must be detailed on the case report form. Other clinical trial drugs were prohibited during the study.

Combination therapies are prohibited as follows:

1) Similar anti-HER2 therapeutic drugs.

Drug-drug interaction studies with this product have not been formally conducted in patients. To characterize the potential drug-drug interaction of the free MMAEs, results from another drug-drug interaction study with an ADC drug coupled with the same cytotoxic monomethyl-Australian statin E(MMAE) are presented below:

2) the effect of other drugs on vidicon for injection:

CYP3A4 potent inhibitors: Other MMAE-coupled ADC drugs in combination with ketoconazole, a potent inhibitor of CYP3A4, will increase the exposure of free MMAEs by 25% in Cmax and 34% in AUC; There is no effect on the ADC exposure. It is hypothesized that coadministration of this product with a potent inhibitor of CYP3A4 will have the same effect on exposure to free MMAE and bound antibodies as the ADC drug.

CYP3A4 potent inducers: Other MMAE-coupled ADC drugs in combination with rifampin, a potent inducer of CYP3A4, reduced exposure of free MMAEs by 44% in Cmax and 46% in AUC; There is no effect on the ADC exposure. It is hypothesized that coadministration of this product with a potent inducer of CYP3A4 will have the same effect on exposure to free MMAE and bound antibodies as the ADC drug.

Other drug effects of vidicon mab for injection: CYP3A4 substrates: Other MMAE-coupled ADC drugs in combination with midazolam, a sensitive CYP3A4 substrate, did not affect midazolam exposure. It is also hypothesized that this product will not affect exposures of drugs metabolized by CYP3A4 enzymes.

VII. Study intervention discontinuation/subject discontinuation and withdrawal *

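### Neither the efficacy set nor the pCR definition says how to score pT0N0 after non-study anticancer therapy; as written it counts as a pCR

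*Protocol*

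**What the plan says.** - **Analysis set.** Protocol III.2.2, repeated in 5.4.2, takes every patient who had at least one dose of any study drug "and had a radical cystectomy following that treatment". It states no condition on what happens between the two.
- **Endpoint.** III.3.1 defines pCR as pT0N0 at radical cystectomy. 5.4.3.1 words it differently: cystectomy after neoadjuvant therapy has been completed, with no residual tumour in the investigator's assessment.
- **After progression.** 5.2.2, on the scan before cycle 3: "If the patient had PD, subsequent treatment would be administered at the discretion of the investigator". 5.2.4 likewise leaves later treatment to the investigator when a patient is not suitable for surgery.
- **Evaluability.** For patients with progression or an AE-shortened course who still meet the surgical indication, 5.2.4 says that "surgery will be continued within the specified time frame and will still be considered eligible for treatment and evaluation for all study requirements". Cases beyond the time limits go to the team leader unit, which decides on eligibility for analysis; no criterion is given.
- **Other anticancer therapy.** The exit criteria (IV.1.3) list "4. Combined use of any anti-tumor therapy" among the possible reasons for stopping study treatment. Withdrawal from the study is a separate list. The prohibitions in 6.2 name "1) Similar anti-HER2 therapeutic drugs" and other trial drugs.
- **Timing.** The visit schedule under 5.3.5 places surgery 28 to 42 days after the last dose; 6.1 says 4 weeks after neoadjuvant treatment.

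**The concern.** The trial is meant to attribute pT0N0 to the two study drugs. If a patient stops them, receives something else, and only then has a cystectomy, the specimen reflects the other therapy as well. The written definitions nevertheless credit the result to the study regimen. A patient who progressed on study drug would be an EFS failure and could still be a success on the primary endpoint.

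The protocol does treat the start of new anticancer therapy as an event elsewhere: it closes the safety and AE windows (5.2.3 and the visit-schedule notes) and postoperative follow-up (5.2.5). It plays no part in pCR.

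At stake are two decisions that rest on very small counts. One case can move 1 to 2 of 18 at stage 1 (stop becomes continue) or 6 to 7 of 43 at the end (failure becomes success).

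**Working it through.** **Step 1: is there a rule?** Setting the sections side by side, III.2.2, III.3.1 and 5.4.2 contain no condition on intervening therapy. IV.1.3 stops study treatment but does not take the patient out of the study or the efficacy set. No section scores such a patient as a non-responder. A switcher who later has a cystectomy is thus in the set, and pT0N0 is a pCR.

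**Step 2: how much room is there?** With 21-day cycles, a patient who progresses before cycle 3 had the last study dose at about day 22 and is scanned at about day 43. Surgery at 28 to 42 days after the last dose falls on days 22 + 28 = 50 to 22 + 42 = 64. That is 50 − 43 = 7 to 64 − 43 = 21 days after the scan, or about 1 to 3 weeks.

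**Step 3: reproduce the design.** Inputs from 5.4.1: "The historical control pCR rate was assumed to be 10% based on recent clinical studies"; expected rate 25%; alpha 0.05; 80% (printed as confidence, read as power); 18 patients in stage 1 and 43 in total; continue at 2 or more, succeed at 7 or more; 10% dropout. The Simon optimal design for 10% against 25% has n1 = 18 and N = 43, and 43 / 0.90 = 47.8 gives 48, so the sizes reproduce. With the printed cut-offs,

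P(success) = Σ over x ≥ 2 of P(Bin(18, p) = x) · P(Bin(25, p) ≥ 7 − x),

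which is 0.122 at p = 0.10.

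**Step 4: add switchers.** Let k of the 43 patients switch, placed at random, so that the number in stage 1 is hypergeometric. Each switcher has pT0N0 with probability q; everyone else has 0.10. Scoring switchers as non-pCR is the case q = 0. Both k and q are assumptions. Exact results with the printed cut-offs:

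| k | scored non-pCR | q = 5% | q = 20% | q = 30% | q = 40% |
|---|---|---|---|---|---|
| 1 | 0.111 | 0.116 | 0.133 | 0.144 | 0.155 |
| 2 | 0.101 | 0.111 | 0.144 | 0.168 | 0.192 |
| 4 | 0.081 | 0.101 | 0.169 | 0.222 | 0.280 |

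The gap for two switchers is 0.111 − 0.101 = 0.010 at q = 5% and 0.192 − 0.101 = 0.091 at q = 40%.

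**Step 5: does it depend on the printed cut-offs?** The optimal design continues at 3 of 18 and succeeds at 8 of 43 (alpha 0.048). There, two switchers give 0.059 to 0.084 at q = 20% to 40%, against 0.038 if scored as non-pCR. The gap remains.

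**The case against.** The strongest reply is that the protocol nowhere describes progression, then another therapy, then cystectomy, then evaluation. The evaluability clause in 5.2.4 reads as going on to the planned operation. Where that section mentions non-study treatment, it is for patients who are not operated on, and they are outside the efficacy set. The later treatment in 5.2.2 is undefined and could include surgery itself. A full course of another therapy would normally overrun the surgical window, and late cases are then not included automatically. In addition, 5.4.3.1 ties pCR to completed neoadjuvant therapy, and scoring rules for later therapy are often left to an SAP.

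Most of this stands as to frequency. A reader might infer from the 15-week limit in 5.2.4 that some nine weeks remain after the cycle-3 scan for another regimen. The documents do not support that: the limit caps the duration of neoadjuvant treatment, and the visit schedule leaves about 1 to 3 weeks.

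It does not close the gap. The protocol itself fixes the set and the endpoint, and neither excludes these cases. The completion wording in 5.4.3.1 conflicts with 5.2.4, which keeps patients who stopped early evaluable, so it cannot serve as the missing rule. Referral to the team leader unit has no stated criterion and no requirement to decide before pathology is known, in an open-label trial with investigator-assessed pathology.

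The size is also open to challenge. Switchers have progressed or stopped early, so a q of 20% to 40%, two to four times the 10% historical rate, may be generous. At q = 5% the effect is 1 to 2 percentage points for two to four switchers.

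**Conclusion.** The gap is real: under the current text, pT0N0 after a switch to non-study anticancer therapy counts as a pCR. Compared with scoring such patients as non-pCR, this can only raise the count. It is a low-to-moderate matter because the route is narrow and probably uncommon.

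For two switchers, a true rate of 10% and the printed cut-offs, P(success) is 0.111 to 0.192 for q from 5% to 40%, against 0.101 under the stricter rule. These figures are illustrations, since the documents give no switch rate and no pT0N0 probability after a switch.

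A reader might infer that this gap explains why the false-success rate exceeds 5%. It does not: the rate is already 0.122 with no switchers, because of the printed cut-offs, which is a separate point. Nor do the documents show that the trial's result would be invalid without the change. They show only that a single such case could decide a stage.

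**What to change.** Add to III.3.1 and 5.4.3.1 a sentence of this kind: a patient who receives any anticancer therapy other than the study drugs between first dose and cystectomy stays in the denominator and is counted as not having pCR, whatever the pathology. Apply it to the stage-1 count, the final count and the downstaging rate. Report pT0N0 regardless of switching as a sensitivity analysis.

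Apply the same rule to cases referred to the team leader unit under 5.2.4, and require that eligibility for analysis be decided before the pathology is known. Reconcile the completion wording in 5.4.3.1 with the evaluability of early stoppers in 5.2.4.

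The cost is small. Sample size and treatment do not change. 6.2 already requires all concomitant medications on the case report form, so only non-drug therapy such as radiotherapy may need an added field. The one drawback is that the reported pCR rate may be slightly lower. The wording should be settled before the stage-1 count.

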5.2.3 Drug safety visit

Patients who stop/complete treatment for any reason during new adjuvant therapy are required to return to the hospital for a safety follow-up (28 days after the last dose [-7 to +21] and start the radical surgery, or before starting new anti-cancer therapy (surgery), whichever occurs first; In principle, return to the study center, but also in the local hospital for review). This visit can be combined with other visits. If routine laboratory tests (e.g., hematology, serum biochemistry) were performed prior to the safety visit, it is not considered necessary to repeat the same test in the investigator's experience. Imaging is not required at the safety follow-up if it is less than 28 days from the last imaging.

5.2.4 Surgical treatment

Preoperative evaluation will be performed prior to radical surgery, and if the patient meets the surgical indications, the investigator will perform radical cystectomy at an appropriate time as planned; If the patient is not suitable for surgery, the investigator decides to administer subsequent treatment. Disease progression occurs during the neoadjuvant treatment phase, or the AE fails to complete 4 cycles of neoadjuvant treatment (total neoadjuvant treatment duration does not exceed 15 weeks), but if the investigator assesses that the indication for radical surgery is met, surgery will be continued within the specified time frame and will still be considered eligible for treatment and evaluation for all study requirements. If the investigator determines that physical conditions preclude radical surgery, study treatment will be discontinued, an end-of-treatment visit will be given, and additional treatment selected by the investigator will be continued. If any of the conditions exceed the above time limits, but the investigator determines that the procedure is still acceptable, the team

leader unit will be contacted to determine whether or not they are eligible for study analysis. Patients who discontinue neoadjuvant therapy early due to disease progression or an intolerable adverse event (AE) before surgery and do not undergo surgery are given an end-of-treatment visit and will continue to receive other treatments selected by the investigator.

Patients who are amenable to surgery will receive the following treatment: radical cystectomy. Surgical procedures: Open, laparoscopic or robotic options are available. Resection range: According to the classical resection range, that is, the bladder and the surrounding adipose tissue, and the distal end of ureter. For male patients, the prostate and seminal vesicles should also be included, while for female patients, the uterus, bilateral appendices and part of the anterior vaginal wall should also be included (Note: Female patients are allowed to selectively retain pelvic organs according to the operator's experience and the patient's condition, but the reason should be recorded and explained). Lymph node dissection: The pelvic standard lymph node dissection was required, namely, the dissection of the bifurcation (proximal end) of the common iliac vessel, the genito-femoral nerve (lateral), the iliac circumflex vein and Cloquet lymph node (distal end), and the internal iliac vessel (posterior side), including the obturator lymph node (note: a wider lymph node dissection could be performed in accordance with the patient's condition during the operation, but the reason should be recorded and explained). Urinary diversion was selected according to the operator's experience and the patient's condition.

Perioperative drug use: Unless otherwise indicated as cautious or prohibited in this protocol, the investigator may reasonably use the drug according to experience and the patient's condition. Pathological staging after neoadjuvant therapy was assessed based on surgical samples after radical surgery.

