5.3.5 Visit window

All visits during neoadjuvant therapy were to be within the range of -3 to +7 days of the planned date, and postoperative visits were considered to be 14 days, unless otherwise noted. Evaluations scheduled for the day of study treatment dosing (Day 1) per cycle should be completed prior to study treatment infusion/dosing, unless otherwise noted. Laboratory and imaging results should be reviewed prior to dosing. Scheduling a study visit at a protocol-specified time point that is in conflict with a holiday, weekend, or other event/law will allow the visit to be scheduled to the nearest feasible date.

Visit schedule

	sift	Treatment period (one cycle every 21 days)				Drug safety follow-up r	operation		Postoperative follow-up				
		Cycle 1	Cycle 2	Cycle 3	Cycle 4		Preoperative evaluation	Radical resection	1 week	1 month	3 months (EOT)	6, 12, 18, 24 months	9, 15, 21 months
fate (window)	-28 to -1	one	-3 to +7	-3 to +7	-3 to +7	28 after last dose (-3 to +7)	-7 to 0	28 – 42 after the last dose	±3	±7	±14	±14	±14
Informed consent a	X												
Demographic data/ Treatment historyb	X												
Physical examination/vital signs c	X	X	X	X	X	X	X		X	X	X	X	
ECOG assessment	X	X	X	X	X	X	X		X	X	X	X	
Surgical fitness evaluation	X						X						
Electrocardiogram d	X	X	X	X	X	X	X		X	X	X		
Hematology e	X	X	X	X	X	X	X		X	X	X	X	
Serum biochemistry e	X	X	X	X	X	X	X		X	X	X	X	
Urinalysis e	X	X	X	X	X	X	X		X	X	X	X	
Fecal analysise	X			X			X						

Coagulation e	X						X						
Pregnancy testf	X					X	X						
Hepatitis b two half qualitative g	X						X						
Hepatitis c qualitative g	X						X						
Venereal disease (HIV)g	X						X						
Marker screening (HER2 IHC)	X												
Thyroid functionh	X						X						
Chest CT plain scan i	X			X		X	X				X	X	
Total abdominal+pelvic CT plain scan+enhanced i	X			X		X	X				X	X	
Bladder (or pelvis) Multiparameter mri	X			X			X						
Bone scan i	X												
Previous/concomitant medications	X	X	X	X	X	X	X	X	X	X			
Adverse eventj	X	X	X	X	X	X	X	X	X	X	X		
Vidicon monoclonal antibody administration k		X	X	X	X								
Ampley monoclonal antibody administration l		X	X	X	X								
Radical resection and pathological evaluation m								X					
Archived/fresh tumor histon	X							X					
EQ-5D-5L/ EORTC QLQ-C30 o	X	X	X	X	X	X	X	X	X	X	X	X	
Living condition	X	X	X	X	X	X	X	X	X	X	X	X	X

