5.4.3 Efficacy analysis

Analysis of primary effectiveness endpoint for 5.4.3.1

The primary endpoint, the pathological complete response rate (pCR rate), was defined as the proportion of patients in the efficacy analysis set who received radical cystectomy after completion of neoadjuvant therapy without residual tumor lesions as assessed by the investigator. Will be analyzed based on the validity analysis set.

5.4.3.2 secondary efficacy endpoint analysis

The pathological descending rate is determined according to the pathological results after surgery to determine whether the disease is descending to below T2. The percentages of CT2N0 → PT0N0, CT3-4AN0 → PT0N0, CT2N0 → \leq PT 1N0, CT3-4AN0 → \leq PT 1N0 were calculated respectively, and the 95% confidence interval (CI) of bilateral Clopper-Pearson for pathological stage reduction rate was calculated, to evaluate the accuracy of the estimate of pathological stage reduction rate. Will be analyzed based on the validity analysis set.

Event-free survival (EFS), is the time from the first neoadjuvant treatment until disease progression, death from any cause, or new onset of other tumors. The Kaplan-Meier(KM) method

will be used to estimate the no-event curve and the corresponding quantiles (including median values). If the two-sided 95% confidence interval for the median can be estimated, the generalized Brookmeyer and Crowley method (Brookmeyer and Crowley, 1982) was used. The KM method will be used to estimate EFS rates at 1 and 2 years from the first dose, and 1 and 2 years after surgery, with the corresponding 95% confidence interval estimated using Greenwood's formula (Greenwood, 1926). The EFS deletion criteria will be in compliance with the FDA Industry Guide: Clinical Trial Endpoints for Approval of Cancer Drugs and Biological Products (FDA 2007). EFS will be analyzed based on the security analysis set.

Overall survival (OS) was defined as the time from the start of treatment to death for any cause. OS will perform similar analyses using the KM method above for populations included in the safety and efficacy analysis sets, respectively. The time curve will be plotted against the KM estimate of OS. The median OS, OS rates 1 and 2 years from the first dose, and OS rates 1 and 2 years after surgery will be calculated and show a bilateral 95% CI.

5.4.4 safety analysis

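### Section 5.2.4 lets the team leader unit decide, without criteria, whether a patient operated on outside the time limits is analysed, which conflicts with the definition of the efficacy analysis set

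*Protocol*

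**What the plan says.** Section 5.2.4 of the protocol deals with patients who progress, or who stop for an adverse event, before completing four cycles. If the total neoadjuvant duration is within 15 weeks and surgery takes place in the specified time frame, such a patient "will still be considered eligible for treatment and evaluation for all study requirements".

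The section then turns to cases outside those limits: "If any of the conditions exceed the above time limits" and the investigator still finds the operation acceptable, the team "leader unit will be contacted to determine whether or not they are eligible for study analysis".

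The analysis set is defined twice, in matching terms:

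- Section III, item 2.2, on the condition for membership: "received at least 1 dose of any study drug treatment (any component of neoadjuvant combination therapy) and had a radical cystectomy following that treatment".
- Section 5.4.2: "Includes all patients who received at least 1 dose of any study drug treatment (any component of neoadjuvant combination therapy) followed by radical cystectomy".

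Section 5.4.3.1 says of the primary endpoint, the pCR rate: "Will be analyzed based on the validity analysis set". The visit schedule in section 5.3.5 places surgery at "28 – 42 after the last dose" (days).

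**The concern.** A patient who was dosed and then operated on late belongs to the efficacy set under sections III and 5.4.2. Under section 5.2.4 the same patient may be left out if the team leader unit so decides. Nothing in the protocol says which rule prevails.

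The discretion has no stated limits: no criteria, no deadline, and no requirement that the decision precede the pathology result. The trial is open-label and single-arm, and the investigators assess the pathological stage themselves, so the result is not masked from those involved.

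At stake is the denominator of the primary endpoint. If membership can be settled case by case, the denominator is not fixed in advance and selective exclusion is possible, whether or not anyone intends it.

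**Working it through.** **1. The texts side by side**

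| Question | Sections III (2.2) and 5.4.2 | Section 5.2.4 |
|---|---|---|
| Condition for being analysed | At least one dose, then radical cystectomy | As left, but outside the time limits the team leader unit decides |
| Time limit | None | 15 weeks of treatment; a time frame for surgery that the section does not give |
| Approval step | None | Yes, without criteria |
| Timing relative to pathology | Not applicable | Not fixed |

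Only two sets are defined: safety (all dosed) and efficacy (dosed and operated). There is no per-protocol set to which the 5.2.4 phrase could refer. Leaving a dosed and operated patient out of either set contradicts that set's definition.

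The trigger is also loose. The schedule gives surgery at 28 to 42 days after the last dose, while section 6.1 gives 4 weeks after neoadjuvant treatment.

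**2. The plan's own sample size**

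Inputs from section 5.4.1: p0 = 10%, p1 = 25%, alpha 0.05, power 80% (called confidence there), 10% dropout. The probability of success in a two-stage design with stage 1 cut-off a and final cut-off r is

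P(p) = Σ (x ≥ a) Bin(x; 18, p) × Pr[Bin(25, p) ≥ r − x].

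The optimal Simon design has 18 patients in stage 1 and 43 in total, which matches the protocol. With cut-offs of at least 3/18 and at least 8/43 its alpha is 0.048 and its power 0.800. Allowing for dropout, 43/0.9 = 47.8, so 48. The numbers of patients reproduce. The cut-offs written in section 5.4.1 (at least 2/18 and at least 7/43) give alpha 0.122. That is a separate matter and serves here only as a baseline.

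**3. Possible shift in the estimate**

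The protocol gives no number of late cases. Assume L late cases among 43, with only the late non-responders dropped (the worst direction). The expected estimate is 43p / (43 − L(1 − p)).

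| L | True pCR 10% | True pCR 25% |
|---|---|---|
| 2 | 4.3/41.2 = 10.4% | 10.75/41.5 = 25.9% |
| 4 | 4.3/39.4 = 10.9% | 10.75/40 = 26.9% |
| 6 | 4.3/37.6 = 11.4% | 10.75/38.5 = 27.9% |

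**4. At the success boundary of 7 responders**

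The programme summary sets the level: "the confidence intervals will use a one-sided 95% confidence interval". Using Clopper-Pearson for pCR is an assumption.

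| Non-responders dropped | Estimate | One-sided 95% lower limit |
|---|---|---|
| 0 | 7/43 = 16.3% | 7.9% |
| 2 | 7/41 = 17.1% | 8.3% |
| 4 | 7/39 = 17.9% | 8.7% |
| 6 | 7/37 = 18.9% | 9.2% |

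For comparison, 11/43 = 25.6% has a two-sided 95% interval of 13.5% to 41.2%.

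**5. If dropped patients were also replaced**

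Dropping non-responders does not by itself change a rule based on a count of responders. It would if the excluded patients were made up from the 48 recruited, which is a further assumption. With a share s of operated patients late and only late non-responders replaced, the pCR rate among those analysed is p / (1 − s(1 − p)). At p = 10%:

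| s | Rate among analysed | Type I error, 3/18 and 8/43 | Type I error, 2/18 and 7/43 (as written) |
|---|---|---|---|
| 0 | 0.1000 | 0.048 | 0.122 |
| 5% | 0.1/0.955 = 0.1047 | 0.060 | 0.145 |
| 10% | 0.1/0.91 = 0.1099 | 0.075 | 0.173 |
| 20% | 0.1/0.82 = 0.1220 | 0.118 | 0.246 |

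This is a bound under perfect outcome-based selection, not a prediction.

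**The case against.** The case on the other side has five parts.

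- **The clause may be only operational.** It does not name the efficacy set, which is defined twice elsewhere, and the text is a rough translation. It could be read as an instruction to call the lead centre about a deviation. But the words concern eligibility for analysis, and no other set exists that they could mean.
- **The natural timing is before surgery.** The investigator judges that the operation is still acceptable and then contacts the unit, so pCR would be unknown and could not be selected on directly. This is the likelier reading and it lowers the risk. Nothing in the protocol requires it, however.
- **Late cases may be few.** Four 21-day cycles take 84 days. Using the +7-day window in full at cycles 2 to 4 adds 21 days, giving 105 days, exactly 15 weeks. A patient within the visit windows therefore does not breach the treatment limit. The surgery window may be missed more often, but no frequency is given. The clause may also cover only patients who progressed or stopped early, which would narrow it further.
- **Criteria for deviations often sit in an SAP.** That is true of the criteria. It does not resolve two protocol statements that disagree on who enters the primary analysis.
- **Keeping everyone could credit the study drugs with a pCR reached after other therapy.** A patient with progression before cycle 3 may be given other treatment and operated on much later. The concern is fair, but it is about the existing set definition, which the proposed wording restates and does not widen.

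What stands is that the effect is probably small and its direction unknown.

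**Conclusion.** The concern holds. Section 5.2.4 and the efficacy set definition give different answers for a dosed patient operated on outside the time limits, and the first depends on an unconstrained decision.

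The consequence is modest and cannot be sized from the protocol. With an assumed 2 to 6 late cases in 43 and selection in the worst direction, the estimate moves by 0.4 to 2.9 percentage points. At 7 responders the lower limit stays below the historical 10% throughout. Type I error rises only if excluded patients are also replaced. The number of late cases, the selective exclusion and the replacement are all assumptions.

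The clause should be changed because it concerns the primary denominator of an open-label single-arm trial and is cheap to correct, not because a large bias has been shown.

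**What to change.** Replace the clause in section 5.2.4 with: *Treatment or surgery outside the time limits is recorded as a protocol deviation; every dosed and operated patient remains in the efficacy analysis set.* This follows the definition the protocol already states twice.

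For clarity, section 5.2.4 can refer to the 28 to 42 day surgery window in the visit schedule. A sensitivity analysis without the late patients is optional and can be left to the SAP.

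If the sponsor prefers to keep some exclusions, the alternative is fixed criteria, written into the set definition and applied before pathology is known.

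The cost is one sentence of protocol wording. The sample size of 43 (48 recruited), the stage rules and data collection stay as they are.
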